1.3 Risk-Benefit Assessment

Despite currently licensed CMV-specific antiviral therapies, CMV disease continues to cause significant morbidity and mortality in solid organ transplant recipients and CMV infection may be associated with multiple other clinical outcomes including allograft rejection, decreased graft and patient survival, and an increase in opportunistic infections [Fishman & Rubin, 2007]. In addition, the treatments and associated toxicities can incur significant healthcare costs. Prophylactic valganciclovir is approved for 200 days after transplant in the United States and 100-200 days in Europe and Canada. From 100-200 days, subjects will have a viral load

assessed by central laboratory and treated preemptively per the standard of care at the institution.

ASP0113 appeared to show efficacy in a single Phase 2 trial over multiple secondary endpoints [Kharfan-Dabaja et al, 2012]. The incidence of local reactogenicity may be greater with ASP0113 than placebo. In addition, while there were CPK elevations at the highest dose level in toxicity studies in rabbits, significant damage to the muscle, as determined by CPK elevations greater than 10 x upper limit of normal, has not been observed in humans. One SAE (hypersensitivity/allergic reaction) leading to discontinuation responded well to medical treatment and was deemed not life-threatening. False positive results in the assessment of CMV viral load can occur in subjects receiving ASP0113 with the use of PCR assays that utilize primers targeted at gB and pp65. Such false positive results, if unrecognized, can lead to misdiagnosis and unnecessary initiation of antiviral therapy. It is unknown if false positive results can occur with the pp65 antigenemia assay.

Given the morbidity and mortality associated with CMV infection and treatment, signals of possible efficacy in a phase 2 trial in HCT recipients, ASP0113 warrants further investigation in the prevention of CMV infection in patients receiving a solid organ transplant.

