5.5.2.1 Adverse Events Commonly Associated with Vaccines

The following adverse events have been reported with other vaccines and will be subject to specific monitoring:

- Acute local vaccine reactions including as local pain, redness, swelling or induration
- Acute systemic vaccine reactions including as anaphylaxis and convulsions
- Late vaccine reactions including demyelinating disorders (e.g., Guillain-Barré syndrome, neuritis, neuropathy).

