5.5.2.2 Infection

- Bacterial, fungal and viral infections and the following information will be collected:
Treatment with an antimicrobial agent for a specific clinical syndrome (not prophylaxis)
- Positive cultures, pathologic identification of microbial agents or significant serological changes related to clinical symptoms
- Typical clinical presentation documented by investigator or appropriate consultant.

In addition, the following information should be collected for potential BK viral infections:

- Renal biopsy results, if performed.

Definitions of opportunistic, EBV and BK infections are provided in Appendices 8 and 9, respectively.

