5.5.2.3 Post-Transplant Lymphoproliferative Disorder (PTLD)

Diagnosis of PTLD should be made following review of tissue specimens. The anatomic staging of PTLD will be captured, specifically if the allograft or Central Nervous System (CNS) is involved. PTLD will be classified according to the criteria in Appendix 12. Additionally, if available, ancillary pathologic information related to cell phenotype, clonality, presence of EBV in the tissue specimen, and donor vs. recipient origin will be collected.

Tissue samples should be interpreted by a hematopathologist or pathologist who is familiar with the histopathologic features of PTLD. If as a matter of the subject's routine medical evaluation tissues are examined for the presence of EBV by *in situ* hybridization, the cell of origin (B, T, null, mixed) is determined or radiographic evaluation is performed to document the extent of disease (e.g., CT scans) this information will be captured on the CRF.

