7.6 Analysis of Safety

7.6.1 Adverse Events

Treatment emergent (TE) is defined as the study period of time from the first dose of Study Drug through one year post first Study Drug injection. A TE adverse event (AE) is defined as any AE that started or worsened during the TE period. Unless otherwise stated, all analyses described in this section will be performed on events and measures during this period.

For the purpose of safety assessments in this study, adverse events recorded during the period between the informed consent and the first dose of Study Drug will be classified as Medical History.

The coding dictionary for this study will be the Medical Dictionary for Regulatory Activities (MedDRA). It will be used to summarize adverse events (AEs) by system organ class and/or preferred term. The version of MedDRA to be used will be determined prior to final database lock.

The following summaries of adverse events will be provided by system organ class and preferred term for TE adverse events:

- Number and percentage of subjects with AEs
- Number and percentage of subjects with drug-related AEs
- Number and percentage of subjects with serious AEs
- Number and percentage of subjects with AEs leading to permanent discontinuation of Study Drug injection
- Number and percentage of subjects with serious drug related AEs
- Number and percentage of subjects with drug related AEs leading to permanent discontinuation of Study Drug injection
- Number and percentage of subjects with AEs by severity (worst degree)
- Number and percentage of subjects with drug related AEs by severity (worst degree)
- Number and percentage of subjects with AEs by relationship to Study Drug

Drug-related AE is defined as any AE with at least possible relationship to study treatment as assessed by the investigator or with missing assessment of the causal relationship.

All summaries of serious TEAEs described above will also be performed for serious AEs that were reported any time after the start of Study Drug administration.

The number of deaths and of subjects with AEs of special interest that occur during the TE period will also be summarized.

Subgroups analyses for age group (< 65, ≥ 65), race group (white, black, other), sex (male, female), and the use of anti-thymocyte globulin (ATG) (yes/no) will be performed for the following summaries:

- TEAEs
- Drug-related TEAEs
- Serious TEAEs
- TEAEs leading to permanent discontinuation of Study Drug
- Serious AEs during the study

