7.5.2.3 Acute Systemic Reactions Assessed by Investigators

The symptoms and grading of systemic vaccine reactions assessed by investigators are defined below.

Vital signs are assessed pre- and 1 hour post- each injection. Changes will be used to determine the grades 1-3 according to the charter below. Grade 4 (except for fever related) comes from the SAEs. If any SAE that is considered related to systemic reactions post each injection by the investigators (captured in the CRF) and meets one of the two criteria below will be a grade 4 systemic reaction: (1) PT=Endotracheal Intubation, or (2) PT= Tachycardia, Bradycardia, Hypertension, or Hypotension with NCI- CTCAE v4.03 severity grade \geq 4.

Systemic (General)*	Mild (Grade 1)	Moderate (Grade 2)	Severe (Grade 3)	Potentially Life-Threatening (Grade 4)
Fever (°C)*** (°F)***	38.0-38.4 100.4-101.1	38.5-38.9 101.2-102.0	39.0-40 102.1-104	> 40 > 104
Tachycardia-beats per minute	Increase in heart rate 5-15 beats/minute	Increase in heart rate 16-30 beats/minute	Increase in heart rate > 30 beats/minute	ER visit or hospitalization for arrhythmia
Bradycardia-beats per minute	Decrease in heart rate 5-10 beats/minute	Decrease in heart rate 11-15 beats/minute	Decrease in heart rate > 15 beats/minute	ER visit or hospitalization for arrhythmia
Hypertension (systolic)-mm Hg	Increase in systolic blood pressure (SBP) 20-30 mmHg	Increase in SBP 31 mmHG - 40 mmHg	Increase in SBP > 40 mmHg	ER visit or hospitalization for malignant hypertension
Hypotension (systolic)-mm Hg	Decrease in SBP 5 mmHg	Decrease in SBP 5.1 mmHg to 10.0 mmHg	Decrease in SBP to > 10.0 mmHg	ER visit or hospitalization for hypotensive shock
Respiratory Rate-breaths per minute (at rest)	17-20	21-25	> 25	Intubation

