9.4 Appendix 4: List of the SAP Changes and Rationale

The changes to the approved SAP (15April 2014) that affect the analyses are specified with the rationale in the table below.

SAP Sections	Description	Rationale
5.2 Per Protocol Set (PPS)	Removed.	For a Phase 2 study, this type of analysis where a sizable number of patients are excluded from the PPS classification criteria may provide uninterpretable results.
6.1.2 Secondary Efficacy Endpoints	Removed one of the secondary efficacy endpoint of subject survival through one year.	In order to avoid redundancy as as the mortality is summarized as a part of adverse event summary.
7.1 General Consideration	Specified the analysis duration of the primary study period as data collected through day 380 (=365+14+1) for this SAP.	This analysis duration is specified by taking the protocol allowed visit windows in order to clarify the data inclusion for this analysis plan.
7.2.2 Protocol Deviation	Removed the category of PD5-Other.	In order to capture the protocol deviations to specific categories utilizing PD1 through PD4.
7.4.1.2 Sensitivity Analysis for Primary Efficacy Endpoint	
 Clarified the analysis to assume a patient with at least 2 consecutive missing central laboratory viral load as a CMV viremic, and Added an analysis to consider a patient who took AVT that is adjudicated as a CMV viremia treatment but no evidence of CMV viremia by central laboratory is assumed CMV viremic. 	These sensitivity analyses are planned in order to evaluate the robustness of the primary analysis for the primary efficacy endpoint.
7.4.3 Analysis of Exploratory Endpoints	The assessments of kidney transplantation and SF-12 questionnaires to be only listed without a formal analysis within this analysis plan.	A proper analysis for these questionnaires to be conducted by the HEOR expert.
7.5.2 Adverse Events of Special Interest	Removed the following AEs of special interest: 
 Opportunistic infections Special infections related to kidney transplant Post-transplant lymphoproliferative disorder 	The opportunistic infection is a prespecified exploratory efficacy endpoint thus removed from this section in order to avoid redundancy. The second and third bullet items are removed because these events are not expected to occur under vaccine treatment.

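### SAP 7.5.2 gives no grouped by-arm summary for anaphylaxis, convulsions, EBV/BK infection or PTLD, although the protocol names them as events of special interest and commits to summarising such events

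*SAP*

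**What the plan says.** **Protocol.** Section 5.5.2 lists the events of special interest:

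- Section 5.5.2.1 includes "Acute systemic vaccine reactions including as anaphylaxis and convulsions" and "Late vaccine reactions including demyelinating disorders (e.g., Guillain-Barré syndrome, neuritis, neuropathy".
- Section 5.5.2.2 covers infections: "Definitions of opportunistic, EBV and BK infections are provided in Appendices 8 and 9, respectively".
- Section 5.5.2.3 is given over to PTLD: "Diagnosis of PTLD should be made following review of tissue specimens". Classification follows Appendix 12.

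Section 7.6.1 then makes the reporting commitment: "The number of deaths and of subjects with AEs of special interest that occur during the TE period will also be summarized".

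**SAP.** Section 7.5.2 covers local reactions, diary-reported fatigue, myalgia and fever, vital-sign reactions assessed by the investigator, and late vaccine reactions. Apart from fever, a Grade 4 systemic reaction in 7.5.2.3 must be a related SAE coded either as endotracheal intubation or as "Tachycardia, Bradycardia, Hypertension, or Hypotension with NCI- CTCAE v4.03 severity grade" 4 or higher. Appendix 4 records that three categories were taken out of 7.5.2. Opportunistic infections went because they are already an exploratory efficacy endpoint. Special kidney-transplant infections and PTLD went because "these events are not expected to occur under vaccine treatment".

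**The concern.** Safety is the second of the trial's two stated objectives, and the protocol chose in advance which events deserved specific monitoring. The SAP drops some of these without comment and others for a reason that does not justify dropping them. EBV and BK infection and PTLD are events of the transplant population and can occur in either arm. An expectation that the vaccine does not cause them is a hypothesis, and tabulating them by arm is how it would be checked.

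Allergic events matter here for a further reason. Protocol 1.3 reports of the earlier experience that "One SAE (hypersensitivity/allergic reaction) leading to discontinuation responded well to medical treatment", and protocol 6.1.1 makes anaphylaxis of Grade 3 or higher a criterion for stopping study treatment. Without a group defined beforehand, a reader of the study report would have to assemble the relevant terms after unblinding, and that choice would be post hoc.

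**Working it through.** The plan attaches no figure to this point, so the check is mainly a comparison of texts. The only design number used is 70 subjects per arm (protocol 7.1, SAP 4).

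**1. Protocol categories against SAP 7.5.2**

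| Protocol 5.5.2 category | Grouped by-arm summary in SAP 7.5.2? |
|---|---|
| Acute local reactions | Yes, 7.5.2.1 |
| Anaphylaxis | No |
| Convulsions | No |
| Late reactions (demyelinating disorders) | Yes, 7.5.2.4 |
| EBV and BK infection | No; removed per Appendix 4 |
| PTLD | No; removed per Appendix 4 |

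The current text of 7.5.2 confirms these absences, so the finding does not rest on the change log.

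**2. The Grade 4 rule.** The non-fever rule in 7.5.2.3 admits five preferred terms: intubation and four vital-sign terms. An SAE that the investigator attributes to a systemic reaction but that is coded as anaphylaxis or as a convulsion would not count.

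**3. What SAP 7.5.1 still provides.** All, drug-related, serious, drug-related serious and discontinuation-leading events are tabulated by system organ class and preferred term for each arm, with a further table by preferred term alone. So each event has a row by arm. The rows do not add up to subjects. As a hypothetical case, suppose hypersensitivity, urticaria and bronchospasm each show a count of 1 in an arm. The number of subjects affected is anything from 1 to 3, that is, from 1/70 = 1.4% to 3/70 = 4.3%.

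The discontinuation table narrows this only partly. The stopping criterion covers Grade 3 or higher, and a reaction after the fifth and last dose leaves no dose to discontinue.

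**4. Definitions.** Appendix 9 places presumptive BK nephropathy under BK infection, and Appendix 12 sorts PTLD into categories. Preferred-term rows apply neither.

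**5. The opportunistic-infection route.** Protocol Appendix 8 lists EBV conditions, PTLD and BK virus. SAP 7.4.3 compares the number of opportunistic infections between arms by Poisson regression. However, both branches of its search require the system organ class of renal and urinary disorders. Read literally, this may miss EBV disease and PTLD. It would also yield one combined count, not a figure for each condition.

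**6. What a restored table could show.** The documents give no event rates, so a range is assumed. The chance of at least one affected subject in an arm is 1 − (1 − p)^70:

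| Assumed rate p | Chance of at least one |
|---|---|
| 0.5% | 30% |
| 1% | 51% |
| 2% | 76% |
| 5% | 97% |

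For k affected subjects against 0, the two-sided Fisher p is 2 × C(70,k)/C(140,k). This gives 0.058 for k = 5 and 0.028 for k = 6. Only a split of 6 against 0 or wider falls below 0.05, so the tables would be descriptive.

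**The case against.** The strongest reply is that nothing is lost. A reader of Appendix 4 might infer that these events are never compared by arm. That is wrong, because SAP 7.5 presents all safety data by arm on the safety set and 7.5.1 gives every event a preferred-term row. This part of the reply stands in full.

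Other parts also stand:

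- **Zero counts.** With no events, the one-sided 95% upper limit is 1 − 0.05^(1/70) = 4.2%, and it follows equally well if every relevant row is zero. Grouping matters once counts are above zero.
- **The earlier reaction.** It is tempting to read it as anaphylaxis. Protocol 1.3 calls it hypersensitivity or allergic and not life-threatening, and protocol 5.5.2.1 names anaphylaxis only. Hypersensitivity terms are therefore an addition to the protocol list.
- **The protocol's promise.** Section 7.6.1 commits to summarising subjects with events of special interest. It does not prescribe one table per category.
- **The change log.** It covers only changes since the SAP of 15 April 2014, which is not available here, so its silence on anaphylaxis and convulsions shows nothing about intent. The removal of PTLD and the special infections is disclosed.
- **EBV and BK ascertainment.** Appendix 9 defines these infections largely by viral load. Neither assay is in the assessment schedule or protocol Appendix 2, and BK biopsy results are collected only where a biopsy was done. Counts would reflect local testing.
- **The infection search.** Cases are classified individually before unblinding, and what the search misses depends on the MedDRA hierarchy, which is not in the documents.

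The reply does not restore the grouped summary, does not apply the protocol's own definitions, and does not rescue a rationale that presumes no vaccine effect.

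**Conclusion.** The point holds as a departure from the protocol's safety-reporting commitment. Four event groups (anaphylaxis, convulsions, EBV/BK infection, PTLD) lack a defined by-arm count of subjects. It does not hold as a loss of the arm comparison, since the single-term rows remain. No efficacy analysis other than the exploratory opportunistic-infection count is touched.

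The conclusion rests on reading 7.5.2 and the 7.4.3 search literally, and on these events being coded under their own preferred terms. It should be corrected before unblinding, because the value of the grouping lies in fixing it without sight of treatment. It would not change what 70 subjects per arm can demonstrate about rare events.

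**What to change.** In SAP 7.5.2, restore subject counts and percentages by arm on the safety set, with worst CTCAE grade, for:

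- (a) anaphylaxis, with related hypersensitivity terms shown as an addition prompted by the earlier allergic SAE;
- (b) convulsions;
- (c) reported EBV infection or disease, and BK infection or nephropathy, by protocol Appendix 9, with a note that ascertainment depends on local testing;
- (d) PTLD by protocol Appendix 12.

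Fix the term lists before unblinding, as 7.5.2.4 already does for late reactions by review before hard lock. In 7.4.3, extend the opportunistic-infection search beyond the renal and urinary class so that it covers the Appendix 8 list. Label the tables as descriptive.

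The cost is SAP wording, term lists and one or two tables from events already reported. No new assessments are needed.

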- AEs of special interest during the study

All AEs will be listed.

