7.6.2 Clinical Laboratory Evaluation

Analyses of clinical laboratory data will be performed on laboratory evaluations during the study.

Clinical laboratory tests (e.g., hematology, biochemistry) will be summarized using mean, standard deviation, minimum, maximum and median for each treatment group at each

scheduled visit. Additionally, the change from baseline will be summarized by treatment group and visit.

The shift in select laboratory tests from baseline (or final visit for renal function tests) to select time points (worst value during study, Months 1, 2, 3, 6, 9, and 12) will be summarized.

Potentially clinically significant (PCS) laboratory test results that are observed any time during the TE period will be tabulated and compared across all treatment groups using a chi-square test. This analysis will be conducted only on subjects that did not meet the PCS criteria at baseline.

Subgroups analyses for age group (< 65 , ≥ 65), race group (white, black, other), sex (male, female), and the use of anti-thymocyte globulin (ATG) (yes/no) will be performed for the following summaries:

- Summary of clinical laboratory tests at each scheduled visit
- Summary of change from baseline at each scheduled visit
- Summary of PCS laboratory values

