7.6.3 Vital Signs Evaluation

Vital signs (oral temperature, systolic and diastolic blood pressure, weight, respiration rate and pulse rate) will be summarized using mean, standard deviation, minimum, maximum and median for each treatment group at each scheduled visit. Additionally, the change from baseline in these parameters will be summarized by treatment group and visit.

The number and percent of subjects that had a systolic blood pressure ≥ 160 mmHg at any time will be tabulated by treatment group for subjects whose baseline value was < 160 mmHg. Subjects that did not have a baseline measurement will be excluded from the analyses. The number and percent of subjects that had a diastolic blood pressure ≥ 100 mmHg at any time and whose baseline value was less than 100 mmHg will be summarized similarly.

The analysis of vital signs described above will also be performed by the following subgroups: age group (< 65 , ≥ 65), race group (white, black, other), sex (male, female), deceased donor and the use of anti-thymocyte globulin (ATG) (yes/no).

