7.2.6 Transplant Information

The following characteristics of the transplant procedure will be summarized by treatment for the SAF.

- Use of anti-thymocyte globulin (ATG) (Yes/No)
- Type of transplant (living donor & ATG=Yes/ living donor & ATG=No/ deceased donor & ATG=Yes/ deceased donor & ATG=No)
- Recipient and donor relatedness (living related donor, living unrelated donor, deceased donor)

- Donor demographics (age, gender, race)
- Recipient and donor HLA typing
- HLA cross match at time of transplant (see [Appendix 1](#) for how the cross match is determined)
- Recipient and donor ABO types
- Recipient and donor Hepatitis B virus, Hepatitis C virus, and Epstein-Barr Virus serostatus, if available, and HCV PCR RNA, (if available)
- Organ preservation method

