7.4.1.3 Subgroup Analysis of Primary Efficacy Endpoint

Subgroup analysis on the primary efficacy endpoint will be performed with a logistic model including treatment, subgroup, and treatment by subgroup interaction as explanatory variables. A subgroup with a level that has fewer than 10 patients within any treatment group, the level will be excluded from the interaction test while descriptive statistics will be provided. If none or only one level of the subgroup meets the 10-subject criterion no subgroup analysis will be performed. The proportion, odds ratio per subgroup factor and its 2-sided 90% confidence intervals will be calculated. As this is a phase 2 study and the interaction test between the treatment group and the subgroup factors should be interpreted with a caution, the p-value from the interaction test will be compared to 0.15.

The subgroup analysis will be performed for the FAS according to:

- levels of randomization strata
- use of ATG, alemtuzumab, or rituximab after randomization
- use of ATG after randomization
- use of alemtuzumab after randomization
- use of rituximab after randomization
- use of alemtuzumab or ATG after randomization
- kidney preservation method (cold, PUMP)
- age group (<65, ≥ 65)
- race (white, black, other)

- gender (male, female).

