7.5 Analysis of Safety

All analysis of safety will be presented by treatment group for the SAF.

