7.5.3 Clinical Laboratory Evaluation	Removed the shift summary for laboratory parameters using low, normal and high normal ranges.	The laboratory values are summarized for the change from baseline using the descriptive statistics.

7.5.3 Clinical Laboratory Evaluation	Removed the following: 
 • Potentially clinically significant (PCS) laboratories • Shift tables for SGOT, SGPT, Platelets, Hematocrit, Hemoglobin, Serum creatinine, and Total bilirubin at granular categories 	This type of analysis is considered medically not meaningful.
7.5.3.1 Liver Function Test	The criteria are updated to the following: 
 • ALT or AST > 3xULN, > 5xULN, > 10xULN, >20xULN • ALT > 3xULN, > 5xULN, > 10xULN, >20xULN • AST > 3xULN, > 5xULN, > 10xULN, >20xULN • ALP > 1.5xULN, >3xULN • Total Bilirubin >2xULN • ALT or AST > 3xULN and Total Bilirubin > 1.5xULN • ALT or AST > 3xULN and Total Bilirubin > 2xULN • ALT or AST > 3xULN and ALP < 2xULN and Total Bilirubin > 2xULN 	These new criteria are the sponsor's standard categories.
7.5.4 Vital Signs	Removed the summary of potentially significant vital signs based on special criteria.	The vital sign is summarized for the mean change from baseline using the descriptive statistics.
7.8 Subgroups of Interest	Removed the subgroup analysis on adverse events of special interest for the various subgroup factors.	This type of subgroup analysis on potentially small number of patients with AEs of special interest may yield uninterpretable results.

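### SAP 7.5 contains none of the safety subgroup summaries promised in Protocol 7.6.1 to 7.6.3, and the one reason given for dropping any safety subgroup covers special-interest events only

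*SAP*

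**What the plan says.** Protocol 7.6.1 names age group, race group and sex as subgroup factors and continues "and the use of anti-thymocyte globulin (ATG) (yes/no) will be performed for the following summaries". Six summaries follow: TEAEs, drug-related TEAEs, serious TEAEs, TEAEs leading to permanent discontinuation of study drug, serious AEs, and "AEs of special interest during the study". Protocol 7.6.2 applies the same four factors to three laboratory summaries: values by visit, "Summary of change from baseline at each scheduled visit", and potentially clinically significant (PCS) values. Protocol 7.6.3 states "The analysis of vital signs described above will also be performed by the following subgroups", using those factors plus deceased donor.

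SAP 7.5 opens with "All analysis of safety will be presented by treatment group for the SAF", and nothing in 7.5.1 to 7.5.6 breaks safety down further. The only subgroup section in the body of the SAP is 7.4.1.3, which begins "Subgroup analysis on the primary efficacy endpoint will be performed with a logistic model". SAP 7.2.6 tabulates ATG use as a transplant characteristic but does not cross it with safety.

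SAP Appendix 4 has one entry on safety subgroups: "Removed the subgroup analysis on adverse events of special interest for the various subgroup factors". The stated rationale is that few subjects may have these events, so results might not be interpretable.

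**The concern.** SAP 7.1 says that all analyses and summaries are generated according to the SAP. It has no clause that carries over protocol analyses the SAP omits. The planned tables will therefore lack summaries that the protocol says will be performed. Protocol 7 and SAP sections 1 and 7.1 have the study report explain departures from the SAP. None of them asks for an explanation of where the SAP departs from the protocol, so the gap could reach the report without comment.

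Safety is one of the trial's two objectives, and ATG use before randomization is one of the two stratification factors. Amendment 2 revised the safety subgroup lists and kept ATG in them, so the commitment is not leftover text. SAP 7.4.1.3 also keeps efficacy subgroups by randomization strata, age, race and gender. The same variables are thus judged usable for benefit but are not used for harm. What is at stake is that a difference in adverse events concentrated in one stratum would be seen only after dilution in a pooled table.

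**Working it through.** The plan gives no figure on this point to reproduce. The check is a side-by-side comparison, followed by arithmetic on assumed rates.

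**Step 1. Protocol commitments against the SAP.**

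| Protocol subgroup summary | In SAP 7.5? | Reason in SAP Appendix 4 |
|---|---|---|
| TEAEs | No | None |
| Drug-related TEAEs | No | None |
| Serious TEAEs | No | None |
| TEAEs leading to discontinuation | No | None |
| Serious AEs during the study | No | None |
| AEs of special interest | No | Yes: small numbers |
| Laboratory values by visit | No | None |
| Laboratory change from baseline | No | None |
| PCS laboratory values | No | Indirect: parent summary removed, with a reason |
| Vital signs | No | Indirect for the threshold summaries; none for the descriptive ones |

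Count: 6 adverse-event + 3 laboratory + 1 vital-sign = 10 promised, 0 retained. No reason is given for 5 adverse-event summaries, 2 laboratory summaries and the descriptive vital signs.

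**Step 2. Does the stated reason extend?** It is specific to the small number of subjects with special-interest events. The documents give no TEAE or serious-TEAE rate. However, Protocol 5.5.8 and Appendix 11 list serious events anticipated in this population regardless of drug exposure, and SAP 7.5.1 plans tables of TEAEs reaching 5% in an arm. Nothing suggests that TEAEs overall are too sparse to divide by a yes/no factor.

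**Step 3. Dilution on assumed rates.** Assume an event rate of 10% on placebo throughout, and on vaccine 30% in ATG subjects and 10% in the others. With ATG share s, the pooled vaccine rate is 0.30s + 0.10(1 − s).

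| s | ATG subjects per arm (of 70) | Pooled vaccine rate | Pooled difference | Difference within ATG |
|---|---|---|---|---|
| 0.30 | 21 | 16% | 6 points | 20 points |
| 0.50 | 35 | 20% | 10 points | 20 points |
| 0.70 | 49 | 24% | 14 points | 20 points |

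**Step 4. What a restored table could show.** Assume 35 subjects per cell and serious TEAEs in 21/35 (vaccine) against 12/35 (placebo) with ATG, and 12/35 in both arms without. The Wald standard error is √[p₁(1 − p₁)/n₁ + p₂(1 − p₂)/n₂].

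- Within ATG: 0.600 − 0.343 = 0.257, SE 0.115, 95% CI 0.031 to 0.483.
- Pooled: 33/70 − 24/70 = 0.129, SE 0.082, 95% CI −0.033 to 0.290.
- ATG effect minus non-ATG effect: 0.257 − 0 = 0.257, SE √(0.115² + 0.113²) = 0.162, 95% CI about −0.06 to 0.57, p about 0.11.

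The pooled table halves the difference. The direct comparison of strata is still inconclusive, even in an example chosen to show a contrast.

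**The case against.** The strongest objection concerns the change log. A reader might infer that Appendix 4 is incomplete, or that the wider removal went unrecorded. The documents do not support that. Appendix 4 lists changes from the SAP approved on 15 April 2014, not departures from the protocol, and that SAP is not supplied. If its subgroup section covered only special-interest events, the log is complete. The log also accounts for the PCS laboratory and vital-sign threshold summaries, whose subgroup versions fall with them. This stands, so the point rests on Protocol 7.6 against SAP 7.5 and not on the log.

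Second, the rates and the ATG share above are assumptions, and on those figures the contrast between strata does not reach conventional significance. This stands too. The illustration shows dilution and predicts nothing.

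Third, the sponsor's stated concern in Amendment 2 is that ATG, a T-cell depleting agent, may reduce vaccine effectiveness. That is an efficacy concern, and the SAP keeps efficacy subgroups. No document says that ATG subjects are at greater risk of vaccine harm. This is correct, but the protocol names ATG as a safety subgroup factor whatever the motive.

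Fourth, other routes exist: Protocol 7.6.1 plans listings of all AEs, and the data monitoring committee reviews safety under its charter. These could reveal a pattern, but they do not replace a planned table by arm. Finally, the SAP is signed before unblinding, so nothing suggests that the omission was driven by data.

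**Conclusion.** The inconsistency is real. The protocol promises ten safety subgroup summaries and the SAP contains none. Special-interest events have a direct reason. PCS laboratory values and the vital-sign thresholds are covered through their parent tables. Nothing explains the absence of the rest, and the small-numbers argument does not reach TEAEs or serious TEAEs.

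The consequence is limited. The primary analysis, type I error and sample size are unaffected. A reader might infer that a harm confined to ATG subjects would go undetected. The documents support less: it would not be tabulated in the planned SAP tables, and pooling could dilute it by an amount that depends on an ATG share the documents do not give. Restored tables would flag such a pattern for medical review but would not establish it. The change should be made because it keeps a protocol commitment on a stated objective at little cost.

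**What to change.** In SAP 7.5.1, restore the Protocol 7.6.1 subgroup summaries for TEAEs, drug-related TEAEs, serious TEAEs and TEAEs leading to discontinuation, at minimum by ATG, and by age, sex and race. State that they are descriptive.

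Define ATG use explicitly. Use before randomization is preferable, because it is the stratification factor and treatment cannot affect it. Amendment 2, however, explains the protocol's safety-subgroup wording as ATG at any time, so the choice needs a sentence.

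For serious AEs during the study, laboratory values and changes by visit, and descriptive vital signs, either restore the subgroup summaries or state in the SAP why they depart from the protocol. The deletion for special-interest events can stand.

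The cost is repeating existing tables by existing variables. The drawback is small cells in some age and race groups, which should be read with that in mind.
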